Stimulation Frequency and Intensity. The decisions to use 10 Hz rTMS and to stimulate both hemispheres is based on a recent meta-analysis of AD trials, which reported that the cognitive efficacy of rTMS was larger when high frequency (≥ 10 Hz) rTMS was used, and when stimulation was bilateral or to the right hemisphere (Liao et al., 2015). The decision to use an intensity of 120% magnetic field intensity relative to the participant's resting motor threshold (MT) is also based on a strategy to achieve efficacy in the older population without compromising safety. Early studies used lower intensity stimulation because of safety concerns at the time, which have now been alleviated with greater experience. This intensity is safe, tolerable, and has been necessary and sufficient to overcome the effect of age-related cortical atrophy (Nahas et al., 2004). Recent rTMS studies of cognitive enhancement that targeted the older population used intensity levels ranging from 90% MT to 120% MT, depending on the site selected for treatment stimulation (Hsu et al., 2015). 120% is the intensity used in the AD, mild TBI, and depression clinical trials, directed by our Co-Investigators, Drs. [name], [name], and [name].

Stimulation Pattern and Session Duration: The 10 Hz pulse frequency will be patterned as a 4-second train (40 pulses) with an 11-second interval between trains, which is repeated over a period of 25 minutes (i.e. a total of 4,000 pulses per session: 40 pulses per train x 4 trains per minute x 25 minutes). Prior studies generally used 1,900 pulses or less per session, in line with 2009 safety recommendations (Rossi, Hallett, Rossini, Pascual-Leone, & Safety of TMS Consensus Group, 2009). The lack of serious adverse effects seen with 1,900 pulses has motivated clinical investigators focused on the target population of treatment-resistant major depressive disorder (TRMDD) to deliver an efficacious course of treatment safely, but in a shorter period of time. We note that MagVenture received 510(k) FDA clearance in June 2017 to use "... a range of inter-train intervals from 11 to 26 seconds" in delivering the 10 Hz / 3000 pulse, FDA cleared protocol for treatment of adults with TRMDD.

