A 10 Hz 4-sec train, 10-sec ITI protocol that delivered a total of 4,000 pulses during a 23-minute session was used in the VA 9-site depression trial (VA CSP #556; PI: [name]), which completed data collection in 2016. Although detailed safety and efficacy data are not available as of August 2017, the CSP #556 PI and Co-Chair [name] state that no seizures occurred in CSP #556 (per email communicated to the PI and DSMB members). Study co-investigators, Drs. [name] and [name], have adopted a 10 Hz 5-sec train, 10-sec ITI protocol for use in their currently ongoing rTMS clinical trials for treatment of cognitive impairment due to mild AD and mild TBI. The DSMB of the present trial has advised stricter adherence to the published safety table (Rossi et al., 2009). In summary, we have selected a 10 Hz 4-sec train, which is within the safety table, and an 11-sec ITI, which is 1 sec longer than that used in CSP #556.

Delivery schedule. Delivery of the study intervention will be scheduled as two rTMS sessions per treatment visit, with 10 treatment visits scheduled M-F during two consecutive weeks. This delivery schedule was documented to be safe and effective in a depression-treatment trial (Loo, Mitchell, McFarquhar, Malhi, & Sachdev, 2007) (10 Hz, 110% intensity, 1,500 stimuli per session). This “twice-daily” procedure is being used at our site by Co-Investigators Drs. [name] and [name] in two ongoing clinical interventional studies (10 Hz, 120% intensity, 4000 stimuli per session). From a patient’s perspective, a twice-daily intervention that requires a 2-week commitment is likely to be more convenient than coming to a clinic M-F for 4 weeks, particularly if there is some flexibility for “make-up” sessions, e.g. when the participant needs to fulfill other commitments.

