In summary, the 10 Hz stimulation protocol to be used in this study will consist of delivering up to 8,000 magnetic pulses per day, with a total of 80,000 pulses over 2 to 2.5 weeks. This is within the range of 60 to 90,000 total pulses that is delivered in FDA-approved rTMS treatment of TRMDD (e.g. 3,000 magnetic pulses per day, 5 days per week, for 4 to 6 weeks) and more than the 39,000 pulses delivered by the NeuroAD™ Therapy System protocol (Rabey & Dobronevsky, 2016; Rabey et al., 2013). Our experience, based upon clinical research involving more than 60 AD and mTBI study volunteers, is that the stimulation protocol to be used in this study will be a safe, tolerable, and efficient means of providing noninvasive brain stimulation, provided that safety screening and other precautions are taken to minimize the risks of rTMS.

Summary of the known and potential risks of the rTMS study intervention:

The serious known and potential risks of rTMS are:

- Inadvertent induction of a seizure (less than 1 in 1000 patient exposures);
- In the absence of careful screening, ferromagnetic implants, objects or electromechanical devices such as pacemakers are serious risks

Other known and potential risks of rTMS are:

- Discomfort at the site of rTMS stimulation (15% of patients);
- Mild to moderate headaches (up to 30% patients), and the
- Possibility of temporary hearing loss if ear protection is inadequate.

For detailed information on risks of rTMS, see Study Protocol Section 7 “SAFETY ASSESSMENTS.” See also, the original IRB protocol submission and informed consent form, approved by the Stanford IRB Panel 3, March 14, 2017.

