5.2 Schedule and Procedures for Administering the Study Intervention

Schedule. The intervention will be administered as 20 weekday sessions during a period of 2 to 4 weeks, depending on scheduling constraints. Typically, a participant will have a morning session and an afternoon session. At the study physician's discretion and if the participant requests, up to three rTMS sessions can be scheduled per day with at least a one-hour interval between sessions.

Intervention sessions are scheduled as a 1-hour blocks, to allow time for late arrivals, for assessments of adverse effects, and for the 25-minute rTMS intervention. The intervention will be administered in outpatient clinic setting. In all, the participant will receive a total of 20 rTMS sessions.

Procedures for administering the rTMS Intervention

1. Motor Threshold Determination. Prior to administering the intervention, the participant's right and left motor threshold (MT) will be measured to standardize the stimulation intensity to be 120% of resting MT, i.e. $1.2 \times \text{MT}$. The 120% intensity will be specific to the MT of each hemisphere. The TMS Operator will determine the left MT at the end the screening visit, and the right MT at the beginning of Session 1 of the Intervention Phase. The TMS Operator will record the right and left MTs—and the corresponding stimulation intensities equal to 120% of right and left MT—on the participant's TMS Intervention Log (described in Section 6.2.3). The participant's right MT will also be recorded within the TMS system in association with the participant's randomization treatment number. (The device software allows for one MT to be saved per participant.)

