As in Ahmed et al (Ahmed et al., 2012), rTMS will be applied over the right hemisphere first, immediately followed by rTMS over the left hemisphere. Rabey et al. (2013) also used a R, L order for the two bilateral regions. In both studies, all participants will receive the same order. It is beyond the scope of this study to investigate order effects. Given the absence of *a priori* data on this point, this study will follow the methods of the two prior studies (Ahmed et al., 2012; Rabey et al., 2013) and stimulate the right, immediately followed by the left.

TMS Stimulation Parameters for the active DLPFC and active LPC rTMS intervention groups will be: 10 Hz, 4-second train duration and 11-second inter-train interval. During each session, 2,000 pulses will be applied for each hemisphere (for a total of 4,000 pulses per session). These parameters will be pre-programmed in the device at the outset of the clinical trial, before the TMS operator begins administering the intervention.

Modifications and supportive care in case of difficulty tolerating the intervention. As noted previously, headache, scalp discomfort at the site of stimulation are relatively common, although tolerance to these adverse effects generally develops over the first 5 to 10 sessions of TMS therapy (Perera et al., 2016). Should a headache or site discomfort occur, these symptoms are expected to be self-treated, e.g. with ibuprofen. Discomfort can vary depending on intensity and location. For better tolerability, intensity can be ramped up from 80% to 120% during the first two sessions, and study staff may be able to move the coil position slightly if dental pain occurs.

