6.2.3 Intervention Visits (Visits 3 – 12)

A participant will receive a total of 20 rTMS intervention sessions within a period of 2 to 2.5 weeks, depending on scheduling constraints. Typically, a participant will have a morning session and an afternoon session during a one-day clinical visit. Accordingly, 2

intervention sessions are recorded as a single “visit” and the visits are numbered from Visits 3 through Visit 12.

The first intervention session (Visit 3) needs to take place during a window of 7 ± 3 days after the completion of the Baseline assessments. An Intervention session is scheduled as a 1-hour block to allow time for late arrivals, assessment of adverse effects, and for the 20-minute rTMS intervention. At the study physician’s discretion and if the participant requests, up to three rTMS sessions can be scheduled per day with at least one hour between sessions.

To be fully adherent, the participant should complete 20 sessions within 30 calendar days.

The following assessments and procedures will be performed at the Intervention Visits:

First Intervention Session (am, Visit 3: *Overnight fasting is necessary*)

- Concomitant Medications (update of previously recorded medications)
- Adverse Events (to capture a new or a worsening pre-existing condition)
- Vital Signs
- Fasting Blood Sample (Genetic and BDNF Biomarkers), followed by breakfast
- rTMS Safety Questionnaire
- Motor Threshold Determination (Right Hemisphere), as described in Section 5.2*
- rTMS Intervention Log
- Administration of study intervention, as described in Section 5.2
 - * *Motor thresholds will be rechecked at the study physician’s direction at subsequent intervention sessions in the event a change in medication or a change in sleep pattern is reported by the participant and/or study partner. If a participant’s subsequent MT is greater than the capacity of the TMS device, the subject will be treated at the maximum device capacity and tracked as such.*

Second Intervention Session (pm, Visit 3)

- Concomitant Medications
- Adverse Events
- rTMS Safety Questionnaire if more than 24 hours since the previous
- rTMS Intervention Log
- Administration of the study intervention

Intervention Sessions 3-18 (Visits 4 – 11)

- Concomitant Medications
- Adverse Events
- Vital Signs
- rTMS Safety Questionnaire
- rTMS Intervention Log
- Administration of the study intervention

Intervention Session 19 (am, Visit 12: *Overnight fasting is necessary*)

- Concomitant Medications

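### Section 2.2 states a maximum of 8,000 pulses per day, but Sections 5.2 and 6.2.3 permit three 4,000-pulse sessions, or 12,000, on up to six days of a course

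*Combined protocol and SAP*

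**What the plan says.** Section 2.2 closes its account of the stimulation parameters with a summary: the protocol "will consist of delivering up to 8,000 magnetic pulses per day, with a total of 80,000 pulses over 2 to 2.5 weeks". The same paragraph judges, from clinical research with more than 60 volunteers and on condition that safety screening and other precautions are applied, that "the stimulation protocol to be used in this study will be a safe, tolerable, and efficient means of providing noninvasive brain stimulation".

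The session dose is given twice. Section 2.2 builds it up as "40 pulses per train x 4 trains per minute x 25 minutes". Section 5.2 gives 2,000 pulses per hemisphere, "for a total of 4,000 pulses per session".

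For the delivery schedule, Section 2.2 describes two sessions per visit over ten weekday visits. It cites two precedents, both twice-daily: a published depression trial ("10 Hz, 110% intensity, 1,500 stimuli per session") and two ongoing studies at the site ("10 Hz, 120% intensity, 4000 stimuli per session").

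The operative sections allow more. Section 5.2 says that "up to three rTMS sessions can be scheduled per day with at least a one-hour interval between sessions", and Section 6.2.3 that "up to three rTMS sessions can be scheduled per day with at least one hour between sessions". Both require the participant to ask and the study physician to agree.

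**The concern.** The daily figure in Section 2.2 is worded as an upper limit, and it stands in the paragraph that draws the safety conclusion. A reader who judges the daily dose from that paragraph is assessing 8,000 pulses. A participant in an active arm who is treated exactly as Sections 5.2 and 6.2.3 allow can receive half as much again on a given day.

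Seizure is among the serious risks that Section 2.2 lists. The section also records that the DSMB advised stricter adherence to the published safety table. A daily maximum is therefore a figure that should agree across the protocol and carry a stated basis. What is at stake is whether those who approved the regimen, and those who consent to it, were given its true daily ceiling. The estimands, the analysis and the sample size are not affected.

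**Working it through.** **Inputs**
- Train: 10 Hz for 4 seconds, followed by an 11-second interval (Sections 2.2 and 5.2).
- Session length: 25 minutes (Sections 2.2 and 5.2).
- Course: 20 sessions (Sections 5.2 and 6.2.3).
- Sessions per day: two as standard (Section 2.2), up to three permitted (Sections 5.2 and 6.2.3).

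**Reproducing the plan's figures**
- Pulses per train: 10 × 4 = 40. Trains per minute: 60 / (4 + 11) = 4.
- Session: 40 × 4 × 25 = 4,000, which agrees with 2 × 2,000 in Section 5.2.
- Standard day: 2 × 4,000 = 8,000, as stated.
- Course: 20 × 4,000 = 80,000, as stated.

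**The permitted maximum**
- Three-session day: 3 × 4,000 = 12,000, and 12,000 / 8,000 = 1.5.
- The course stays at 80,000, because the number of sessions is fixed at 20.
- No text in the supplied documents lowers the pulses per session on a three-session day.

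**Sensitivity to session length.** Section 6.2.3 once calls the session 20 minutes long, against 25 elsewhere. At 20 minutes a session would be 40 × 4 × 20 = 3,200 pulses and three would give 9,600. That is still 9,600 / 8,000 = 1.2 times the stated maximum, so the conflict does not depend on that slip.

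**How often it can occur.** Six three-session days use 6 × 3 = 18 sessions and leave 2; a seventh would need 21. Six is therefore the ceiling. To finish inside ten weekdays with *k* of them missed, the number of three-session days needed is 20 − 2(10 − *k*) = 2*k*:

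| Weekdays missed | Three-session days needed | Weekdays available |
|---|---|---|
| 1 | 2 | 9 |
| 2 | 4 | 8 |
| 3 | 6 | 7 |
| 4 | 8 | 6 (not possible) |

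**Precedents on the same daily scale.** The depression trial gives 2 × 1,500 = 3,000 pulses a day. The site's ongoing studies give 2 × 4,000 = 8,000. Neither reaches 12,000.

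**Slack under a cap of two sessions a day.** The course then needs 10 weekdays.
- Treatment starts on Day 7, with Days 7–11 and 14–18 taken as Monday to Friday (Table 2): 23 weekdays to Day 37, so 23 − 10 = 13 can be missed.
- Treatment starts on Day 10, taken as a Monday (the end of the 7 ± 3 day window in Section 6.2.3): 20 weekdays to Day 37, so 20 − 10 = 10 can be missed.

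**The case against.** The strongest reply is that this is a loose phrase and not a dosing fault. The arithmetic in Section 2.2 is right for the standard schedule that it describes. Sections 5.2 and 6.2.3 agree with each other, so staff following them face no conflicting instruction. Most of the safety argument rests on intensity, train length, inter-train interval, pulses per session and course total. None of these changes on a three-session day, and 80,000 stays within the 60,000 to 90,000 range that Section 2.2 cites. The DSMB's recorded advice concerned the safety table, and the protocol answers it through train length and interval. The third session needs a request, a physician's agreement and at least an hour's gap. Side effects are asked about at every session (Section 7.3), and the operator watches for seizure activity (Section 7.1.4).

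All of that stands, and it limits the point. It does not make 8,000 the maximum. It also does not supply a precedent for three such sessions in a day.

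A reader might go further and infer any of the following, none of which the documents support:
- *The regimen is unsafe at 12,000 a day.* Nothing supplied shows harm at that dose.
- *High-dose days are unlimited.* The 20-session course caps them at six, and nothing forces even those: Section 5.2 allows up to four weeks and Table 2 allows make-up sessions through Day 37.
- *The DSMB never accepted the third session.* The protocol carries a DSMB approval date of November 30, 2017, and the only modification annotated in the supplied text is the removal of the Attention Network Task. On that record the clause was in the approved protocol. Whether the board considered 12,000 specifically cannot be told.

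**Conclusion.** The inconsistency is real and should be corrected. The permitted daily maximum is 12,000 pulses, 1.5 times the figure in Section 2.2, on at most six days of a 20-session course. The basis that Section 2.2 gives for its delivery schedule covers two sessions a day only.

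This rests on each session delivering the full 4,000 pulses, as Section 5.2 specifies, and it concerns real magnetic pulses, so it applies to the active arms. It is a statement about the supplied text. Appendix IV, which holds the step-by-step operating procedures, and the original IRB submission and consent form, to which Section 2.2 refers for detailed risks, were not available. A limit or a justification may be set out there.

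**What to change.** Correct Section 2.2 to read 'typically 8,000 and up to 12,000 magnetic pulses per day', give the safety basis for 12,000, and ask the DSMB to confirm that figure explicitly. Check that Appendix IV and the participant information agree. In the same edit, change the 20-minute session in Section 6.2.3 to 25 minutes; this is clerical only. The cost is a sentence or two, a document check and an item for the DSMB. No extra patients are needed, and the scheduling flexibility that Section 2.2 values is kept.

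If no basis for 12,000 can be given, limit Sections 5.2 and 6.2.3 to two sessions (8,000 pulses) per day, with missed sessions made up on further weekdays through Day 37. Some participants would then finish later. The make-up period still absorbs about 13 missed weekdays from a Day 7 start and about 10 from a Monday Day 10 start, so few should be unable to complete the course.

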6.2.4 Follow-up Visits (Visits 13, 14 and 15)

Immediate Post-Treatment (Visit 13)

The Immediate Post-Treatment Visit 13 needs to occur 7 ± 3 days after the 20th and final intervention session.

- Each of the assessments and procedures performed at the Baseline Visit will be repeated at this visit. See Section 6.2.2.

- In addition, the participant and study partner will be asked to complete a brief questionnaire regarding their views on the acceptability of rTMS as a treatment.

Follow-up at 3-Month (Visit 14)

Visit 14 can be completed ± 2 weeks of the target date.

- Vital Signs
- Concomitant Medications
- Adverse Events
- Cognitive Assessment Battery, administered by the Study Coordinator
- ECog and FAQ Functional Outcome Questionnaires completed by Participant and/or Study Partner

6-Month Follow-up (Visit 15)

Visit 15 can be completed ± 2 weeks of the target date.

- Each of the assessments performed at the 3-Month Follow-up will be repeated.
- The Study Completion/Participant Withdrawal Form will be filled out to document the participant's completion of the study.

6.2.5 Study Completions, Withdrawals, Early Discontinuations and Terminations

Study Completions and Withdrawals

Visit 15 serves as the participant's final evaluation. If a participant withdraws from the study before Visit 15, every attempt will be made to collect the reason for the withdrawal of consent. If the withdrawal from the study is due to a Serious Adverse Event (SAE) or Unanticipated Adverse Device Effect (UADE), the participant will be followed by telephone at least every 30 days to monitor recovery or other outcome, until the SAE is resolved. If the SAE or UADE is not resolved, the participant will continue to be followed until 30 days after the End of Study date for that participant. The SAE form will be updated at each contact. Adverse Events (AEs), SAEs, and Adverse Device Effects (ADEs) are defined and discussed in more detail in Section 7.3.

Early Discontinuation of the Study Intervention

If a participant has a seizure during the intervention phase, the intervention will be discontinued immediately and completely. A VA Outpatient Neurology Outpatient Consult evaluation will be requested to provide an understanding of precipitating factors involved in the seizure, and whether follow-up care is needed. Study staff will then follow the participant by telephone to monitor recovery or other outcome, and report this SAE promptly per the appended protocol Appendix VI. "Seizure Protocol."

If it is determined that a participant is using medications or abusing substances that increase risk of having a seizure, the PI and study physician will evaluate the situation and determine if it is appropriate for the participant to continue the intervention. If the study physician or PI feels that it is in the participant's best interest to discontinue intervention because clinical judgment is that the intervention is not safe or tolerable for the participant, the intervention will be discontinued.

In each of these situations that lead to early discontinuation of the intervention, the participant will be asked to undergo the assessments that are normally administered during the Follow-up Phase (i.e. all assessments for Visits 13, 14, and 15).

Early Termination of Participation

Study enrollees are unlikely to be terminated from the study per se, unless an SAE occurs prior to the first rTMS session; or, if after enrollment, the investigators determine that the participant is ineligible.

Documentation of Study Status

Whenever a participant withdraws, is terminated, or completes Visit 15, the **Study Completion/Participant Withdrawal Form** will be filled out to formally document and track the enrollees' study status.

7 SAFETY ASSESSMENTS

7.1 Expected AEs; Safety screening; Modifications and management if an AE occurs

Expected adverse experiences, monitoring of participant safety, and modifications or management in case an AE occurs are described below for each study intervention, in order of procedural flow, starting with the Baseline MRI:

7.1.1 MRI

MRI has potential risks and discomforts but with careful screening of patients and adherence to manufacturer's operation instructions, many adverse events can be prevented (Shellock, 2001; Shellock, 2002).

MRI Safety Screening (Telephone pre-screening; Visits 1, 2, and 13)

Serious adverse events (SAEs) occur if ferromagnetic objects (particularly when implanted) or electromechanical devices such as pacemakers enter the MRI. To assess for MRI Safety, all subjects will be rigorously screened by MR personnel to be certain that they do not have any medical contraindications for MRI which include metallic foreign bodies in the brain or eye, or cardiac pacemaker. This safety screening is part of routine clinical practice at MRI centers and is performed before any subject is permitted to enter the scanning room.

The MRI Safety Form provides screening for factors that might affect the participant's comfort in the MRI environment. These factors include claustrophobia and back pain that interferes with their ability to lie supine for a prolonged period. Individuals who know they are severely claustrophobic would be excluded from participating in the study. People with weight or size above the size allowable by the manufacturer will not be scanned. While it is unlikely that women in this study will be of childbearing age, the formal, written screening form lists pregnancy as exclusion.

Safety Procedures and Modifications during an MRI Scan Session (Visits 2 and 13)

Anxiety. Any participant who experiences anxiety when placed into the MR scanner will be pulled out of the scanner, offered reassurance by the MR tech doing the scan, and offered the option of continuing or terminating the scan. There will be no attempt to

persuade participants to complete a scan that they are uncomfortable with. No sedative or anxiolytic agents will be given, as this is a voluntary research protocol.

Ear Protection. As with a routine clinical MRI, participants will wear MR compatible ear protection.

Incidental findings. The scans performed in this study are not optimized to find abnormalities. However, a Stanford radiologist will provide clinical reads of the anatomical scans and will also notify the PI whether an abnormal finding merits follow-up. In that case, the study physician will contact the participant regarding follow-up with the participant's physician. Image data collected in the course of the research project will not be made available for diagnostic purposes because they do not comprise a full clinical MRI series.

Investigational MRI. Some of the imaging software are not FDA approved, but have been tested for safety and are very similar to what is used regularly in clinical MR examinations. The MR personnel are highly trained in the set-up, monitoring, and use of this software.

Metal. There is a slight risk that someone will accidentally bring metal into the MRI scanner room, which might be pulled into the MRI magnet and injure the participant. MR personnel work with the participant to make sure such objects are removed and stored in a locker before entering the magnet room.

Medical emergency. In the unlikely event of a medical emergency, the Stanford University Hospital's Emergency Department is a nearby, where medical intervention can be provided by Stanford Health Care Emergency Department staff. See Appendix VII. "MRI Emergency Protocol".

